If the amyloid hypothesis is correct, inhibition of cerebral A β accumulation by inhibitors of BACE1 could benefit patients with AD by potentially lowering cerebral A β concentrations and thereby slowing the progression of cognitive decline. Unfortunately, early attempts to develop potent in vivo BACE1 inhibitors were not successful, mainly due to poor brain penetration (Sinha, et al., 1999). Recently, poor blood–brain barrier penetration has been overcome with the development of potent third-generation small-molecule BACE1 inhibitors that exhibit satisfactory pharmacokinetics (PK) and robust cerebral A β reduction in preclinical animal models. As a result of these progresses, several BACE1 inhibitors have entered clinical studies in humans.

Elenbecestat (E2609) is a novel, small-molecule BACE1 inhibitor. Preclinical studies have shown that after oral dosing, elenbecestat inhibits the production of A β 40 and A β 42 in brain (rat and guinea pig) and in CSF and plasma (rat, guinea pig, and monkey). In humans, elenbecestat has been shown to inhibit BACE enzyme activity in CSF thereby lowering CSF levels of amyloid β , including A β (1-x), A β (1-40), and A β (1-42), both in vitro and in vivo in single ascending dose (SAD) and multiple (14 days) ascending dose studies (Elenbecestat Investigator’s Brochure). Another study (study E2609-G000-202; Study 202) has yielded data in subjects with MCI due to AD /Prodromal AD and mild-to-moderate AD dementia (AD-D) administered oral doses of elenbecestat. Interim study data indicated measurable levels of the BACE1 inhibitor in the CSF as well as inhibition of BACE activity and reduction of various forms of A β (eg, 1-x, 40, 42) after daily administration for 4 weeks.

This clinical study, E2609-G000-302 (Study 302), is 1 of 2 studies in the Phase 3 elenbecestat program, and is primarily designed to evaluate the efficacy, safety, and tolerability of elenbecestat in subjects with Early Alzheimer’s Disease (EAD). Confirmation is also required that these subjects meet the NIA-AA core clinical criteria for MCI due to AD or Mild AD. This study is intended to be pivotal for registration and marketing for this patient population.

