- To determine whether elenbecestat is superior to placebo on the Alzheimer's Disease Assessment Scale – cognitive subscale14 (ADAS-cog14), Mini Mental State Examination (MMSE), and Functional Assessment Questionnaire (FAQ) at 24 months in subjects with EAD pooled across studies E2609-G000-301 and E2609-G000-302
- To determine whether elenbecestat is superior to placebo on the ADAS-cog14 Word List (immediate recall and delayed recall) at 24 months in subjects with EAD pooled across studies E2609-G000-301 and E2609-G000-302
- To evaluate the relationship between clinical changes at 24 months (CDR-SB, ADCOMS, ADAS-cog14, MMSE, and FAQ) and changes in biomarkers that reflect disease progression (eg, CSF amyloid beta [A β], total tau [t-tau] and phosphorylated-tau [p-tau], amyloid PET, tau PET, volumetric magnetic resonance imaging [vMRI], and functional MRI [fMRI]) at 24 months in subjects with EAD pooled across studies E2609-G000-301 and E2609-G000-302
- To evaluate the population PK of elenbecestat in subjects with EAD

Biomarker Objectives

- To determine whether elenbecestat is superior to placebo on brain tau pathology at 24 months as measured by tau PET in subjects with EAD (revised per Amendment 04)
- To determine whether elenbecestat is superior to placebo on CSF t-tau and p-tau levels at 24 months in subjects with EAD
- To determine whether elenbecestat is superior to placebo on CSF A β levels at 24 months in subjects with EAD
- To determine whether elenbecestat is superior to placebo on plasma amyloid levels (eg, A β (1-x)) at 24 months in subjects with EAD (revised per Amendment 05)
- To explore potential plasma and CSF biomarkers of AD (eg, neurofilament (NFL), visinin like protein 1 (VILIP1), human cartilage glycoprotein-39 (YKL-40), and neurogranin (Ng) (revised per Amendment 05)
- To evaluate the correlation between the effect of elenbecestat on brain tau pathology with the effect on CSF biomarkers of neurodegeneration at 24 months (revised per Amendment 04)
- To determine whether elenbecestat is superior to placebo on hippocampal atrophy at 24 months in subjects with EAD as measured by changes in hippocampal volume using vMRI

- To evaluate whether elenbecestat is superior to placebo in preserving connectivity at 24 months in subjects with EAD as measured by task free fMRI

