9.2.4 Rationale for Biomarkers

CSF biomarkers, amyloid PET, and tau PET assessments on disease progression at 24 months (and at 12 months for amyloid PET) will be evaluated in substudies of subjects. The CSF substudy is limited to a single timepoint at 24 months to acknowledge the additional burden to the subject that a LP procedure entails. Participation in the substudies is optional and will require specific consent. (revised per Amendment 04)

These aims are discussed below in the context of the individual biomarker assessments to be used in this study.

Briefly, the biomarkers that will be utilized and assessed during this study are:

Soluble Biomarkers in CSF

A β (1-x) captures the effect on the total A β component; therefore, the measurement of this A β isoform most appropriately represents the total pharmacologic effect (A β [1-40] + A β [1-42] and other C-terminally truncated A β peptides such as A β [1-38]) on inhibition of BACE enzyme cleavage.

A β (1-42) measurements in CSF have shown high correlation with results using 11C-Pittsburgh Compound B (PiB), suggesting that CSF A β (1-42) reflects fibrillar A β content (Grimmer, et al., 2009). The aggregation of A β peptides into plaques, and subsequent retention of peptides in the brain parenchyma, accounts for reduced availability of A β to diffuse into the CSF. The decreases seen in AD due to amyloid plaque deposits are related to this decrease.

T-tau and p-tau are sensitive markers of axonal and neuronal degeneration (t-tau) and NFTs (p-tau), and have been demonstrated to increase in parallel with disease progression (Chintamaneni, et al., 2012).

Baseline levels of A β (1-42), t-tau, and p-tau and/or tau: A β (1-42) ratios will also help elucidate the extent of AD pathology at study entry, and can be combined with *ApoE4* genotype in addition to the baseline imaging variables to help explain differences in treatment response between subjects. (revised per Amendment 03)

Amyloid PET

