9.4.4 Selection of Doses in the Study

Selection of elenbecestat 50 mg per day is based on the results (PD, safety, and tolerability) from the completed Phase 1 studies and interim data from the ongoing Phase 2 Study 202. Study 202 has been completed, and a study report is in preparation. It evaluated the PD effects (reduction from baseline in CSF A β levels) along with safety and exploratory efficacy of 5, 15, and 50 mg of elenbecestat given daily. Based on the PK/PD modeling results, elenbecestat 50 mg per day reduced median CSF A β by approximately 70%. (revised per Amendment 02) Based on these data, elenbecestat 50 mg per day dose was selected as a viable dose for this study. Subjects will be stratified according to region (7 levels), clinical dementia staging with no more than approximately 25% of the randomized subjects diagnosed with the early stages of mild dementia due to AD, and concurrent AD medication use.

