The relationship between clinical changes at 24 months (CDR-SB, ADCOMS, ADAS-cog14, MMSE, and FAQ) and changes in each of the biomarkers (amyloid PET, tau PET, CSF A β (1-x), t-tau, p-tau, vMRI, and fMRI) at 24 months, will be evaluated using an ANCOVA model. (revised per Amendments 03, 04, and 05) Changes in clinical scales at 24 months will be the response variables and either continuous or categorical change of biomarkers will be independent variables. The ANCOVA model will also include baseline value for clinical scale as a covariate, with treatment group and randomization stratification variables, as factors. ApoE4 status may be included in the model if appropriate. (revised per Amendment 05)

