promptly. CBCs and percentages will be measured (by a centralized laboratory) every 2 weeks for the first month, and then monthly until month 3 of treatment in the Core Study and until Month 2 in the Extension Phase. Thereafter, they will be monitored every 3 months in the Core Study and every 4 months in the Extension Phase until the end of the Treatment Period and at Follow-up Visits. (revised per Amendment 05)

An assessment of suicidality using the C-SSRS or a clinical assessment of suicidality will be performed at every visit.

AEs that may signal drug abuse potential during the Treatment Period and the first 4 weeks of the Follow-up Period in the Core Study and during the Extension Phase will require a more detailed follow-up. (revised per Amendments 03 and 05)

Other Assessments (Core Study Only)

The NPI-10 item will be conducted at Visit 2 and then every 6 months. HRQoL will be measured using EQ-5D and QOL-AD at Screening and every 6 months following randomization. In order to confirm the validity of the answers provided by the subject, the study partner will serve as subject's proxy and complete the EQ-5D and QOL-AD to rate the subject's HRQoL in addition to the study partner's own EQ-5D. As a result, a set of 3 EQ-5Ds (1 from the subject; 2 from the study partner) and 2 QOL-ADs (1 from the subject; 1 from the study partner) will be provided at each visit. Additionally, the primary study partner burden will be measured using Zarit's Burden Interview every 6 months.

Other Assessments (Extension Phase Only)

The NPI-10 or if available NPI-12 will be conducted at Day 1, Month 4, Month 12, and then every 12 months. If the NPI-12 questionnaire is used, both NPI-10 and NPI-12 scores will be calculated. (revised per Amendment 05)

Bioanalytical Methods (both Core Study and Extension Phase)

CSF AD assessment (eg, tau:A β [1-42] ratio) will be performed for eligibility and treatment response in consenting subjects using validated, commercially available kits. (revised per Amendment 03) Exploratory biomarkers such as neurofilament NFL, Ng, YKL-40, and VILIP1 may also be measured using validated assays. (revised per Amendments 01 and 05)

The *ApoE* genotype for all subjects and NAT2 genotype in a subset of subjects will be determined from blood specimens using validated assays. (revised per Amendment 03)

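### The clinical–biomarker ANCOVA treats CSF Aβ as a marker of disease progression and fits one slope across arms, although elenbecestat lowers CSF Aβ directly

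*Protocol*

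**What the plan says.** **The objective and its model.** Among the other secondary objectives, Section 8.2 sets out to relate clinical change to "changes in biomarkers that reflect disease progression", giving CSF Aβ as one of the examples. Section 9.7.1.6.2 supplies the model: "The relationship between clinical changes at 24 months (CDR-SB, ADCOMS, ADAS-cog14, MMSE, and FAQ) and changes in each of the biomarkers" is to be assessed by ANCOVA. The clinical change is the response and the biomarker change the independent variable. The baseline clinical score is a covariate, treatment group and the stratification variables are factors, and *ApoE4* status may be added. No biomarker-by-treatment term is mentioned. The synopsis describes the same model.

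**The analyte.** The CSF amyloid measure in this ANCOVA is Aβ(1-x) in Section 9.7.1.6.2 and Aβ(1-42) in the synopsis.

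**What the drug does to it.** Section 7 says "elenbecestat has been shown to inhibit BACE enzyme activity in CSF thereby lowering CSF levels of amyloid" β, and goes on to name Aβ(1-x), Aβ(1-40) and Aβ(1-42). Section 9.4.4 reports that "elenbecestat 50 mg per day reduced median CSF A β by approximately 70" per cent.

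**The ratio.** Under Bioanalytical Methods, the synopsis says that the CSF AD assessment, with the tau:Aβ(1-42) ratio as its example, "will be performed for eligibility and treatment response in consenting subjects using validated, commercially available kits".

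**The concern.** A change in CSF Aβ does not mean the same thing in the two arms. On placebo, whatever change occurs comes from the disease and from measurement error. On elenbecestat, most of it is the direct effect of inhibiting the enzyme that makes the peptide. A model with one slope for both arms answers neither of the two useful questions: whether disease-driven change in CSF Aβ tracks clinical decline, and whether deeper suppression on drug goes with slower decline.

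If the two slopes differ in sign, the common slope can be close to zero when both relationships are real. If it is clearly non-zero, it could be read as evidence of disease modification when it reflects variation in exposure among treated subjects. This matters because Section 9.2.1 presents the biomarkers as a way to evaluate whether the drug modifies the disease.

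The difference in analyte adds to the problem. Section 9.2.4 describes Aβ(1-x) as the measure of the total pharmacologic effect, and Aβ(1-42) as reflecting fibrillar amyloid. Which one enters the model changes what is being tested.

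**Working it through.** **1. The plan's own figure.** The fall of about 70% in CSF Aβ is a PK/PD model result. The protocol gives no underlying data, so it cannot be reproduced. It is also stated without an isoform; applying it to Aβ(1-42) is an assumption. Section 7 supports the direction for Aβ(1-42) but gives no size.

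**2. What is compared.** The screening sample is the CSF substudy baseline (Section 9.1.1.1.5) and is taken off drug. The Visit 13 sample is to be taken while the subject is still on study drug (Section 9.5.1.3.3). In the elenbecestat arm the change therefore includes the direct drug effect.

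**3. What the common slope estimates.** Leave the other covariates aside. Let b_E and b_P be the within-arm slopes of clinical change on CSF Aβ change, and S_E and S_P the within-arm sums of squares of CSF Aβ change. With treatment as a factor and no interaction,

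common slope = (S_E × b_E + S_P × b_P) / (S_E + S_P).

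The treatment factor takes out the difference between arm means, so the average drug effect on CSF Aβ does not itself create the slope. What remains is a weighted average of two within-arm slopes, and the arm in which CSF Aβ change varies more gets more weight.

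**4. Why the slopes may differ.** Take CDR-SB, where higher is worse.
- On placebo, with Aβ(1-42): Section 9.2.4 explains low CSF Aβ(1-42) by retention of the peptide in plaque, and says "The decreases seen in AD due to amyloid plaque deposits are related to this decrease". A larger fall would go with more worsening, so b_P would be negative.
- On elenbecestat: if deeper suppression helps, a larger fall goes with less worsening, so b_E is positive. If suppression has no clinical effect, b_E is near zero.

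The average of a negative and a positive (or null) slope has no clear interpretation. With Aβ(1-x), Section 9.2.4 offers no disease-progression reading for the placebo slope at all.

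**5. The price of separate slopes.** Randomization is about 1:1. If CSF Aβ change had equal spread in both arms, each arm would hold half the total sum of squares, so the standard error of a within-arm slope would be 1/√(1/2) = 1.41 times that of the common slope. Unequal spread would move this up in one arm and down in the other.

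**6. The ratio on drug.** Tau rises with disease: Section 9.2.4 says that t-tau and p-tau "have been demonstrated to increase in parallel with disease progression". Aβ(1-42) is low in disease, so a higher ratio reads as more pathology. The fold change is

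(1 + tau change) / (1 − Aβ(1-42) reduction).

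| Assumed fall in Aβ(1-42) | Ratio on drug ÷ baseline, tau unchanged |
|---|---|
| 50% | 1/0.50 = 2.0 |
| 60% | 1/0.40 = 2.5 |
| 70% | 1/0.30 = 3.3 |
| 80% | 1/0.20 = 5.0 |

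With a 70% fall in Aβ(1-42) and tau down 10%, 20% or 30%, the ratio is still 3.0, 2.7 or 2.3 times baseline. Tau would have to fall by 70% to hold it level.

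**The case against.** **A reader might infer that the ratio has been adopted as a response measure, so that an effective drug would be reported as making the disease worse.** The documents do not support this. The sentence is in a bioanalytical paragraph, its subject is the CSF AD assessment, and the ratio is only an example. Table 2 lists the CSF ratio under eligibility alone and shows Aβ(1-x), Aβ(1-42), tau and p-tau separately on treatment. The biomarker endpoints (Section 9.7.1.1.3) and their analyses (Section 9.7.1.7.3) also take t-tau, p-tau, Aβ(1-42) and Aβ(1-x) one by one. No change-in-ratio endpoint, responder rule or test appears.

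**A reader might also infer that the ANCOVA slope simply re-expresses the drug-versus-placebo shift in CSF Aβ.** It does not, because treatment group is in the model. This objection stands in full and limits the concern to unequal slopes and to exposure variation within the treated arm.

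**The SAP may add by-arm slopes or an interaction.** It may. But the protocol has written out the model terms and labelled the marker, and those are what need correcting here.

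**The analyte mismatch may cross versions.** The body carries Amendment 06 consent wording that the synopsis at hand lacks, so the two may come from adjacent versions. The visible Amendment 06 changes concern only consent, and the ANCOVA paragraph in the body has no Amendment 06 tag. The mismatch may therefore be older, but this cannot be confirmed.

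**Conclusion.** The concern holds for the planned ANCOVA. As written, its CSF Aβ slope averages a pharmacologic relationship on elenbecestat with a disease relationship on placebo, under a label that suits only the second. The size of the resulting distortion cannot be given: the protocol supplies no within-arm slopes or spreads for CSF Aβ change, and no size for the CSF substudy. The argument rests on the protocol's own account that the drug lowers CSF Aβ directly. It does not need the 70% to apply to any particular isoform.

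The consequence is for interpretation of an analysis among the other secondary objectives, outside the sequential testing of key secondary endpoints. The ratio wording is a consistency matter. The 2.0- to 5.0-fold rise assumes a 50% to 80% fall in Aβ(1-42) and unchanged tau. No primary, key secondary or listed biomarker endpoint is affected by that wording.

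**What to change.** - In Section 9.7.1.6.2 and the synopsis, name the same CSF Aβ analyte or analytes for the clinical–biomarker ANCOVA.
- For CSF Aβ, estimate the slope separately by arm, or add a biomarker-by-treatment term and report both slopes.
- In Section 8.2 and the synopsis objectives, take CSF Aβ out of the group described as reflecting progression, and state that its on-treatment change is interpreted as target engagement. Table 2 already labels Aβ(1-x) as pharmacodynamic; Aβ(1-42) has no such label.
- In the synopsis Bioanalytical Methods, limit the tau:Aβ(1-42) ratio to eligibility and baseline, in line with Table 2 and the endpoint list. The separate t-tau and p-tau endpoints already cover downstream CSF response.

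The cost is wording in the protocol and the matching analysis specification, and a standard error about 1.41 times larger for each within-arm slope under the equal-spread assumption. No assay, sample or visit changes.

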4 LIST OF ABBREVIATIONS AND DEFINITIONS OF TERMS

Abbreviation	Term
A β	amyloid beta
A β (1-x)	amyloid beta (1-x) (ie, the amyloid beta monomer from amino acid 1 to x [eg 1-42])
AChEI	acetylcholinesterase inhibitor
AD	Alzheimer's disease
ADAS-cog	Alzheimer's Disease Assessment Scale - cognitive subscale
ADCOMS	Alzheimer's Disease Composite Score
AE	adverse event
ALC	absolute lymphocyte count
ALT	alanine aminotransferase
ANCOVA	analysis of covariance
ApoE	apolipoprotein E
APP	amyloid precursor protein
aPTT	activated partial thromboplastin time
AST	aspartate aminotransferase
AUC	area under the concentration \times time curve
BACE1	beta-amyloid converting enzyme 1
BDNF	brain-derived neurotrophic factor
BP	blood pressure
bpm	beats per minute
CBB	Cogstate Brief Battery
CBC	complete blood count
CBP	child-bearing potential
CD33	sialic acid binding immunoglobulin-like lectin 3 (Siglec-3)
CDR	Clinical Dementia Rating
CDR-SB	Clinical Dementia Rating -Sum Of Boxes
CES2	carboxylesterase-2
CFR	Code of Federal Regulations
C _{max}	maximum observed concentration
CI	confidence interval

Abbreviation	Term
CNS	central nervous system
CRA	clinical research associate
CRF	case report form
CRO	contract research organization
CSF	cerebrospinal fluid
C-SSRS	Columbia Suicide Severity Rating Scale
CTA	Clinical Trial Agreement
CTCAE	Common Terminology Criteria for Adverse Events
CYP	cytochrome P450
DSMB	data safety monitoring board
ECG	electrocardiogram
eCRF	electronic case report form
EAD	early Alzheimer's disease.
ED	early discontinuation
ELISA	enzyme-linked immunosorbent assay
EPHA1	erythropoietin-producing hepatoma receptor A1
EQ-5D	EuroQol - 5 Dimensions
FAQ	Functional Assessment Questionnaire (also known as the Functional Activities Questionnaire)
FAS	Full Analysis Set
FDA	Food and Drug Administration
fMRI	functional magnetic resonance imaging
GCP	Good Clinical Practice
GGT	γ -glutamyl transpeptidase
HBsAg	hepatitis B surface antigen
HCVAb	hepatitis C virus antibody
HRQoL	health related quality of life
HSV	herpes simplex virus
ICF	informed consent form
ICH	International Council for Harmonisation of Technical Requirements for Pharmaceuticals for Human Use

Abbreviation	Term
ID	identifier
IEC	Independent Ethics Committee
Ig	immunoglobulin (eg, IgA, IgG, IgM)
INR	International Normalized Ratio
IRB	Institutional Review Board
ISLT	International Shopping List Task
IxRS	interactive voice and web response system
LME	linear mixed effects
LLN	lower limit of normal
LNH	low/normal/high
LP	lumbar puncture
MAD	multiple ascending dose
MCI	mild cognitive impairment
MedDRA	Medical Dictionary for Regulatory Activities
mild AD	mild dementia due to Alzheimer's disease
MMRM	mixed effects model for repeated measures
MMSE	Mini Mental State Examination
MRI	magnetic resonance imaging
N/A	not applicable
NDG	neurodegenerative
NAT2	N-acetyltransferase 2
NIA-AA	National Institute of Aging-Alzheimer's Association
NFL	neurofilament light
Ng	neurogranin
NFTs	neurofibrillary tangles
NPI	Neuropsychiatric Inventory
PBMC	peripheral blood mononuclear cell
PD	pharmacodynamic(s)
PET	positron emission tomography
PGx	pharmacogenomic(s)
pINN	proposed International Nonproprietary Name
PK	pharmacokinetic(s)
PPS	per protocol analysis set
PRN	pro re nata

Abbreviation	Term
PT	preferred term
p-tau	phosphorylated-tau
QD	once daily
QOL-AD	Quality of Life in Alzheimer's Disease
QTc	corrected QT interval
QTcF	QTc interval calculated using Fridericia's formula
R	randomization
RNA	ribonucleic acid
SAD	single ascending dose
SAE	serious adverse event
SOC	system organ class
SUSAR	suspected unexpected serious adverse reaction
SUVR	standardized uptake value ratio
TB	tuberculosis
TEAE	treatment-emergent adverse event
TEMAV	treatment-emergent markedly abnormal laboratory values
TIA	transient ischemic attacks
TREM2	triggering receptor expressed on myeloid cells 2
t-tau	total tau
ULN	upper limit of normal
UNS	unscheduled
VILIP1	visinin like protein 1
vMRI	volumetric magnetic resonance imaging
WBC	white blood cell (count)
WHO DD	World Health Organization Drug Dictionary
YKL-40	human cartilage glycoprotein-39 (HC gp-39)

5 ETHICS

5.1 Institutional Review Boards/Independent Ethics Committees

The protocol, informed consent form (ICF), and appropriate related documents must be reviewed and approved by an Institutional Review Board (IRB) or Independent Ethics Committee (IEC) constituted and functioning in accordance with International Council for Harmonisation (ICH) E6 (Good Clinical Practice[GCP]), Section 3, and any local regulations. Any protocol amendment or revision to the ICF will be resubmitted to the IRB/IEC for review and approval, except for changes involving only logistical or administrative aspects of the study (eg, change in clinical research associate [CRA], change of telephone number). Documentation of IRB/IEC compliance with the ICH E6 and any local regulations regarding constitution and review conduct will be provided to the sponsor.

A signed letter of study approval from the IRB/IEC chairman must be sent to the principal investigator (or if regionally required, the head of the medical institution) with a copy to the sponsor before study start and the release of any study drug to the site by the sponsor or its designee (ICH E6, Section 4.4). If the IRB/IEC decides to suspend or terminate the study, the investigator (or if regionally required, the head of the medical institution) will immediately send the notice of study suspension or termination by the IRB/IEC to the sponsor.

Study progress is to be reported to IRB/IECs annually (or as required) by the investigator or sponsor, depending on local regulatory obligations. If the investigator is required to report to the IRB/IEC, he/she will forward a copy to the sponsor at the time of each periodic report. The investigator(s) or the sponsor will submit, depending on local regulations, periodic reports and inform the IRB/IEC (or if regionally required, the investigator and the relevant IRB via the head of the medical institution) of any reportable adverse events (AEs) per ICH guidelines and local IRB/IEC standards of practice. Upon completion of the study, the investigator will provide the IRB/IEC with a brief report of the outcome of the study, if required.

In the case of early termination/temporary halt of the study, the investigator should notify the IRB/IEC and CA within 15 calendar days, and a detailed written explanation of the reasons for the termination/halt should be given.

